11.5 ADVERSE EVENT ASSESSMENT

11.5.1 Initial Assessment

The investigator must provide the following information:

- Date of onset
- Nature
- Severity
- Duration / date of resolution
- Outcome
- Relationship to investigational device
- Other relevant information

11.5.2 Assessment of Severity

The Investigator must determine the severity of the adverse event according to the following definitions:

- **Mild** The adverse event is noticeable to the subject, but does not interfere with routine activity; the symptoms are easily tolerated and transient in nature.
- **Moderate** The adverse event interferes with routine activity but responds to symptomatic therapy or rest; the symptoms are poorly tolerated and sustained.
- Severe The adverse event significantly limits the subject's ability to perform routine activities despite symptomatic therapy. The adverse event requires medical or surgical treatment or results in hospitalization.
- Life-Threatening The subject is at immediate risk of death.

11.5.3 Device Relatedness

An adverse event is considered device-related when the clinical event has a reasonable time sequence associated with use of the investigational device and is unlikely to be attributed to concurrent disease or other procedures or medications. It is reasonable to believe that the device directly caused or contributed to the adverse event.

The Investigator must provide an assessment of the adverse event according to the following definitions:

- **Definite** The adverse event is clearly related to the investigational device: the event has a temporal relationship to the investigational device, follows a known pattern of response, or is otherwise logically related to the investigational device, and no alternative cause is present.
- **Probable (Likely)** The adverse event is likely related to the investigational device: the event has a temporal relationship to the investigational device, follows a known or suspected pattern of response, or is otherwise logically

related to the investigational device, but an alternative cause may be present.

- **Possible (Unlikely)** The adverse event is unlikely related to the investigational device: the event does not follow a clear temporal relationship to the investigational device or does not follow a known pattern of response, or is otherwise likely to be due to the subject's clinical state or other modes of therapy.
- Not Related The adverse event is clearly not related to the investigational device: the event has no temporal or other relationship to the administration of the investigational device follows no known or suspected pattern of response, and an alternative cause is present.
- Unknown Unable to determine the relationship based on all available information.

11.6 DEVICE DEFICIENCY OR MALFUNCTION

A Device Deficiency is an inadequacy of a medical device with respect to its identity, quality, durability, reliability, safety or performance (includes malfunctions, use errors, and inadequate labeling). Sponsor, in cooperation with the CEC, will assess all device deficiencies that could have led to a serious adverse device effect for potential regulatory reporting requirements.

In the event of a suspected malfunction or device deficiency, the investigational device(s) shall be returned to the manufacture for analysis. Instructions for returning the investigational device will be provided by the Sponsor.

11.7 REPORTING OF DEATH

During the study, all deaths must be reported to the Sponsor within the period outlined in Table 12-1. All deaths also should also be reported on the AE form and End of Study CRF. A copy of the subject's death records, medical records for the events that led to the subject's death, and a death certificate (if available) and an autopsy report (if performed) should be sent to the sponsor. In addition, subject death must be reported to the IRB in accordance with IRB requirements.

12 STUDY ADMINISTRATIVE OVERSIGHT

12.1 CORE LABORATORY

Independent core laboratories shall be utilized to provide a standardized process and assessment of all angiographic and duplex ultrasound studies. The core laboratories will be responsible for analyzing the angiograms and ultrasound images according to the study eligibility criteria, the study endpoints and this study protocol, for providing feedback to the sites and Sponsor regarding

⁰¹⁰⁻⁰⁵⁵ Protocol Version F

the quality of the tracings and images and for providing a written summary report of all angiograms and duplex ultrasound results to the study Sponsor.

Investigators will enroll subjects into the study based on inclusion and exclusion criteria. Lesion characteristics and measurements will be assessed by investigators using visual estimates; however, the core laboratory will assess by quantitative angiography. Baseline measurements and post-procedure results will be reported by the investigator and by the core laboratory.

Angiographic and Vascular Ultrasound Core Laboratory Protocols shall be provided to the investigational sites.

12.2 CLINICAL EVENT COMMITTEE

The Clinical Events Committee (CEC) is an independent adjudication body comprised of qualified physicians who are not participants in the trial. An independent CEC will be utilized for this study. The CEC will be responsible for adjudicating the seriousness and relatedness of all endpoint events and serious device and/or procedure related adverse events occurring during the study period. The CEC will meet regularly. All available data (including lab reports, films, discharge reports, etc.) will be available to adjudicate the events. The committee will also review and rule on all deaths that occur throughout the trial. The composition, guiding policies, and operating procedures governing the CEC are described in a separate CEC Manual of Operations.

12.3 IRB APPROVAL

The study protocol shall be reviewed and approved by the investigator's IRB prior to subject enrollment. The Sponsor must review any proposed changes to the investigational informed consent prior to implementation.

Prior to shipment of investigational devices, a signed copy of the IRB approval letter identifying the clinical study and investigational site is required to be submitted to the Sponsor. Investigators are responsible for obtaining and maintaining annual renewal of the study by their IRB (or according to renewal schedule imposed by the IRB). Evidence of renewal and continued IRB approval must be provided to the Sponsor accordingly.

12.4 INFORMED CONSENT

Informed consent is mandatory and must be obtained from all subjects per local regulations, prior to their participation in the study. Only IRB approved informed consent may be used.

It is the responsibility of the Investigator to ensure written informed consent from each subject, or the legally authorized representative of the subject, is obtained prior to the initiation of any study-related procedures.

⁰¹⁰⁻⁰⁵⁵ Protocol Version F

Subjects who agree to participate in this study will do so voluntarily. They will be treated on an equal basis with all other patients. Choosing not to participate will not affect their care in any way.

Study personnel fully knowledgeable in the purposes and procedures of the study will approach all prospective study participants. The facilities and settings in which prospective participants will be presented with the opportunity to learn about and consent to participation in the study will provide them sufficient quiet and unhurried time to be informed of the study, to ask questions, and between consent being given and the initiation of study procedures. Study personnel will, after presenting the study to prospective participants, assess the subject's understanding and autonomy by asking the subject to explain the study in his/her own words.

Once that step is completed, consent will be able to be given by the subject's signing the consent form. A copy of the consent form will be given to all consented participants.

Original signed subject consent forms must be retained in the study files by the Investigator, and available for review by the Sponsor and/or regulatory agencies, as applicable.

The informed consent form and any other written information provided to subjects will be revised whenever important new information becomes available, or if there is an amendment to the protocol which necessitates a change to the content of subject information and/or to the consent form. The Investigator will inform the subject of changes in a timely manner, and will ask the subject/patient to confirm his/her continuation in the study by signing a revised consent form.

Any revised informed consent form and other written information provided to subjects must receive IRB, Sponsor, and regulatory agency approval, as applicable.

12.5 RECORDS

Each Investigator must maintain the following accurate, complete, and current records relating to the conduct of the study investigation. The final responsibility for maintaining such records remains with the Investigator. These records include, but not limited to:

- All signed agreements;
- IRB/EC approval letter(s);
- Signed ICF;
- Records of AEs, including supporting documents;
- Records of protocol deviations, including supporting documents
- Records showing receipt, use and disposition of all investigational devices, including:
 - o Date, quantity, model and serial numbers of devices received,
 - Name of person(s) who received, used or disposed of each device,
 - The number of devices returned to the Sponsor and the reason(s) for return;
- Key correspondences related to the study;

- Records of each subject's case history, including study-required CRFs, signed ICF, all relevant observations of AEs, the condition of each subject upon entering and during the course of the investigation, relevant medical history, the results of all diagnostic testing, etc.;
- Study personnel visit log;
- Signature authorization and delegation log; and,
- Any other records that applicable regulation requires to be maintained.

The Investigator will maintain all essential trial documents and source documentation that support the data collected on the study subjects in compliance with FDA's GCP guidelines. Documents must be retained until at least 2 years have elapsed since the date the investigation is completed or terminated or the records are no longer required to support a regulatory submission, whichever date is later. These documents will be retained for a longer period of time by agreement with Sponsor or in compliance with other regulatory requirements. The investigator will take measures to ensure that these essential documents are not accidentally damaged or destroyed. If for any reason the investigator withdraws responsibility for maintaining these essential documents, custody must be transferred to an individual who will assume responsibility. The Sponsor must receive written notification of this custodial change.

12.6 REPORTS

Table 12-1 lists those reports that are the investigator's responsibility to deliver to the Sponsor. Each study investigator must follow the EC/IRB reporting requirements for their respective site. If applicable regulations or EC/IRB requirements mandate stricter reporting requirements than those listed, the stricter requirements must be followed.

Type of Report	Prepared by PI for	Reporting Time Frame
UADE	Sponsor, EC/IRB	As soon as possible but no later than 5 working days of knowledge
Death	Sponsor, EC/IRB	Written reports (e.g., via e-mail) within 48 hours
SAE	Sponsor EC/IRB, if required	Within 10 working days of knowledge Per IRB requirement
Device malfunction with clinical sequelae	Sponsor EC/IRB, if required	Within 48 hours via written communication. Return the device to sponsor within 48 hours.
Serious protocol deviations (e.g., ICF not obtained, to protect the life	Sponsor, EC/IRB	As soon as possible but no later than 5 working days of knowledge

Table	12-1:	Reports	Required	from	Investigators	to Sponsor
Inore		reports	negunea		in , congreens	vo sponsor

⁰¹⁰⁻⁰⁵⁵ Protocol Version F

Type of Report	Prepared by PI for Reporting Time Fran	
or physical well-being of a subject in an emergency)		Per IRB requirement
Withdrawal of EC/IRB approval	Sponsor	Within 5 working days of knowledge
Annual progress report	Sponsor, EC/IRB	Annually
Interim report	Sponsor, EC/IRB	Within 14 days of 30-day follow up
Final report	Sponsor, EC/IRB	Within 3 months of study completion or termination
Note: Each IRB/EC may require more stringent reporting requirements that those listed in this table.		

Table 12-2 lists those reports that are the sponsor's responsibility and timelines to report to the FDA and reviewing ECs/IRBs.

Type of Report	Report to	Reporting Time Frame	
UADE	FDA and all ECs/IRBs	Within 10 working days from the time the Sponsor first learns of the	
Withdrawal of IRB/EC Approval or other action on part of the IRB/EC that affects the study	FDA, all ECs/IRBs, and all investigators	Within 5 working days after receipt of the withdrawal of approval.	
Withdrawal of FDA approval	all ECs/IRBs and all investigators	Within 5 working days after receipt of notice of the withdrawal of FDA approval.	
Current investigator list	FDA	At 6-month intervals. Submit the first list 6 months after FDA approval.	
Device Recall	Investigators, ECs/IRBs and FDA	Within 30 working days after the request is made.	
Progress Reports	ECs/IRBs and FDA	At least yearly.	
Inappropriate Informed Consent	FDA	Investigator's report submitted within 5 working days of receipt of notice of such use.	
Study Closure	ECs/IRBs and FDA	Within 30 working days of the completion or termination of the investigation.	
Final Report	Investigators, ECs/IRBs and FDA	Within 6 months of study closure.	

Table 12-2: Sponsor Reporting Responsibility

⁰¹⁰⁻⁰⁵⁵ Protocol Version F

12.7 INVESTIGATOR RESPONSIBILITIES

- Agree to sign and adhere to the Investigator Agreement.
- Obtain approval from the IRB including subsequent protocol amendments and changes to the Informed Consent form and obtaining annual IRB approval and renewal throughout the duration of the study.
- Await IRB approval, as well as, any additional hospital requirements prior to requesting written informed consent from any potential study subject or prior to allowing any subject to participate in the study.
- Complete and provide signed copies of all required investigator documentation such as an Investigator Agreement or Disclosure of Financial Interest.
- Agree to participate in Investigator meetings as scheduled by the Sponsor.
- Be willing to perform and be capable of performing treatment procedures as outlined in this protocol.
- Comply with all required elements of this protocol (e.g., perform testing and followup as specified, especially during personnel transitions).
- Agree to obtain written Informed Consent before any study specific procedures are performed in accordance with GCP.
- Be willing to change hospital routine if required by protocol (as long as subject safety and well-being is not compromised).
- Control any investigational device(s) stored at their site.
- Be aware of, and comply with, GCP and applicable regulatory requirements.
- Permit monitoring and auditing by the Sponsor, and inspection by the appropriate regulatory authorities.
- Have available an adequate number of qualified staff and adequate facilities to properly conduct the study.
- Ensure study personnel are adequately informed about the protocol, the investigational device and study-related duties and functions.

12.8 SPONSOR RESPONSIBILITIES

The Sponsors responsibilities in the study include:

- Selecting the Principal Investigator(s), all clinical investigators and study sites, and other consultants (e.g., monitors) who participate in the study.
- Provide study protocol, device, and GCP training to participating study sites, in quantities sufficient to support study activities, per agreements executed with the study sites.

- Select all qualified clinical Investigators and study sites and other consultants (e.g., the study monitors) who participate in the study.
- Provide financial support to each study site.
- Follow/promote all regulatory standards per appropriate regulations for study sites, core laboratories, and other participants, and ensure compliance by periodically monitoring sites.
- Ensure completion of site monitoring of clinical data at each clinical study site.
- Retain ownership of all clinical data generated in this study, and control the use of the data for appropriate purposes only.
- Review and approve publication of study results in the literature

12.9 PROTOCOL DEVIATIONS / VIOLATIONS AND MEDICAL EMERGENCIES

A protocol deviation or violation is a failure to comply with the requirements of the clinical study as specified in the protocol. Examples of protocol deviations include late visits, missed visits, required follow-up testing not completed. An example of a major protocol violation includes enrollment of a study subject who fails to meet inclusion/exclusion criteria as specified in the protocol. Each investigator shall conduct this clinical study in accordance with the study protocol and any conditions required by the reviewing IRB.

Deviations/violations from clinical protocol requirements will be reviewed and evaluated on an ongoing basis and, as necessary, appropriate corrective actions put into place. See Table 12-1: Reports Required from Investigators to Sponsor for reporting timelines for emergency deviation.

12.10 PRE-STUDY DOCUMENTATION REQUIREMENTS

Prior to shipment or receipt of investigational product, the following documents must be provided to Cardio Flow, Inc.:

- Signed and dated Clinical Trial Agreement
- Signed and dated Investigator Agreement
- Signed and dated Protocol Signature Page
- A copy of the written IRB approval of the protocol
- A copy of the written IRB approval of the Informed Consent Form
- Signed and dated Curriculum Vitae of the Investigator(s)
- Copy of the Investigator(s)' current medical license(s), or equivalent
- Signed and dated Non-disclosure Agreement(s), if required

• Signed and dated Certification/Financial Disclosure Form(s)

12.11 CRITERIA FOR TERMINATING STUDY

The Sponsor reserves the right to terminate the study but intends only to exercise this right for valid scientific or administrative reasons and reasons related to protection of subjects. Investigators and associated IRB will be notified in writing in the event of termination.

Possible reasons for study termination include:

- The discovery of an unexpected, significant, or unacceptable risk to the subjects enrolled in the study.
- A decision on the part of the Sponsor to suspend or discontinue development of the device.

12.12 PUBLICATION POLICY

The data and results from the study are the sole property of the Sponsor. The Sponsor shall have the right to access and use all data and results generated during the clinical study. The Investigators will not use the clinical study/investigation-related data without the written consent of the Sponsor for any other purpose than for clinical study/investigation completion or for generation of publication material, as referenced in the Clinical Trial Agreement/Investigator Agreement.

The Sponsor acknowledges that the study Investigators intend to publish the results of the clinical investigation. The Sponsor shall use all reasonable efforts to collaboratively ensure the appropriate publication or dissemination of the conclusions of the study, and Investigators shall not publish results derived from their institution until the combined results from the entire investigation has been published in a joint, multi-center publication.

Sponsor must receive any proposed publication and/or presentation materials for publications at least 30 days prior to the proposed date of the presentation or the initial submission of the proposed publication in order for the materials to be reviewed by the Sponsor in compliance with the Sponsor's publication policy set forth in the Clinical Trial Agreement/Investigator Agreement.

The Sponsor is responsible for registering the Clinical Investigation on www.clinicaltrials.gov. Institution(s) and/or Principal Investigator(s) shall not take any action to register the study.

13 REVISION HISTORY

Description
Initial release, Version A
Version B. Per FDA's recommendations, following sections have been updated.
1. Added a primary effectiveness endpoint – Technical Success and a hypothesis test for the primary effectiveness endpoint.
 Updated the primary safety endpoint – Freedom from MAE at 30 days and the hypothesis test for the primary safety endpoint.
3. Updated the sample size per hypothesis test.
4. Included an enrollment ceiling per site.
5. Updated statistical analysis section.
 Modified Inclusion Criteria #5 and Exclusion Criteria #9 and 10 for clarity.
Version C. Per site-requested clarifications, the following sections have been updated.
1. Modified Exclusion Criteria #5, 9, and 11 for clarity.
Version D. The following sections have been updated.
 Modified Components of MAE definition #4, #5, to remove ambiguities.
2. Modified Inclusion Criteria #5b for clarity, #5c to align with other published studies.
3. Modified Exclusion Criteria #4 to align with other published studies and #19 for clarity.
Version E. The following sections have been updated.
 Modified Components of MAE definition #4, #5 back to Revision C wording.

01-APR-2020	Version F. The following sections have been updated.
	 Added Cardio Flow FreedomFlow[™] Orbital Circumferential Atherectomy System – Electric to the investigation list.
	 Added device descriptions of the Cardio Flow FreedomFlow[™] Orbital Circumferential Atherectomy System - Electric.
	3. Clarified sample size allocations.
	4. Increased investigational site to 15.
	 Clarified procedure for performing the atherectomy using either pneumatic or electric system.

## **1** INTRODUCTION

This statistical analysis plan (SAP) describes the planned statistical analyses for the clinical investigation "*Evaluation of the Cardio Flow* **F***reedomFlow*TM *Orbital Circumferential* **A***therectomy* **S***ystem to* **T***reat Peripheral Artery Disease (FAST II Trial)*"

This SAP should be read in conjunction with the study protocol and case report forms (CRFs) for details of study conduct and data collection. This version of the plan is developed based upon the study protocol version F, dated February 04, 2020. If a future protocol amendment necessitates a substantial change to the statistical analysis of the trial data, this SAP will be amended accordingly. Amendments to this document will be finalized prior to database lock (DBL).

## 2 STUDY DESIGN

The FAST II study is a prospective, multi-center, non-randomized single-arm study designed to evaluate the safety and effectiveness of the FreedomFlowTM Orbital Circumferential Atherectomy System in subjects diagnosed with peripheral arterial disease of the lower extremities.

The study may enroll up to 112 subjects and will be conducted at up to 15 investigational sites in the United States with approximately 56 patients using the Pneumatic System and approximately 56 patients using the Electric System.

Enrollment is expected to take approximately 6 months with observation periods at time of procedure, pre-discharge, 30 days, and 6 months post-procedure follow-up.

## **3** INTERIM ANALYSES

No formal interim analyses are planned. Early stopping of the trial for effectiveness will not be permitted.

A 30-day primary endpoint report will be prepared and submitted to FDA for the 510(k) clearance. A final report will be prepared following the study completion.

## 4 DETERMINATION OF SAMPLE SIZE

The sample size is calculated to simultaneously power for the primary effectiveness and primary safety endpoints by comparing to the pre-specified Performance Goal (PG).

Primary Effectiveness Endpoint

Sample size estimates were calculated for the primary effectiveness outcome by comparing the technical success rate to the pre-specified performance goal of 86% (i.e., H0: technical success rate  $\leq 86\%$  vs. Ha: technical success rate  $\geq 86\%$ ). The performance goal of 86% was derived using a random effect meta-analysis based on the technical success rates that were obtained from the results of recent atherectomy studies and the allowed 10% margin. The underlying technical

success rate was assumed 96%. Under an exact, one-sided test for a single binomial proportion, at the 0.025 significance level, a sample size of 101 mITT subjects will be required to provide 90% power to meet this technical success objective.

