## Primary Safety Endpoint

Literature review through a random effect meta-analysis showed a 95% freedom from MAE at 30 days. The pre-specified performance goal for the primary safety endpoint is 85% based on an allowed 10% margin. The hypotheses are H0: Freedom from MAE at 30 days  $\leq$  85% vs. Ha: Freedom from MAE at 30 days > 85%. Under an exact, one-sided test for a single binomial proportion at the 0.025 significance level, a sample size of 102 mITT subjects will be required to provide at least 90% power to meet this primary safety objective.

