## Overall Sample Size

In order to adequately power for both primary effectiveness and primary safety hypotheses, we require a sample size of 102 mITT subjects who complete 30 days follow-up. The dropout rate of mITT subjects is assumed to be 10 %. The final sample size for the study will be 112 subjects.

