## 6.2 **Primary Endpoints**

The study will be considered a success if both primary effectiveness and safety objectives are met using the mITT Set at the one-sided 0.025 level of significance in the final analysis. The primary endpoint analyses will also be performed in the PP set as a supportive evidence. The primary endpoint analyses will also be performed in the mITT and PP sets by product power type (Pneumatic System and Electric System).

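### The effectiveness power at 101 subjects is 95.0%, not the stated 90%, and no joint power is given for a success rule that needs both endpoints

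*SAP*

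**What the plan says.** SAP section 4, protocol 8.1 and the protocol synopsis size the two primary endpoints one at a time.

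- **Effectiveness.** Technical success is tested against a goal of 86% with an assumed rate of 96%. The method is given as "Under an exact, one-sided test for a single binomial proportion, at the 0.025 significance level", and the result is that "a sample size of 101 mITT subjects will be required to provide 90% power".
- **Safety.** The goal is 85%. The assumed rate comes from a meta-analysis that "showed a 95% freedom from MAE at 30 days". The plan asks for 102 mITT subjects for at least 90% power.
- **Overall.** The section opens by saying that the size serves both endpoints at once, and closes: "In order to adequately power for both primary effectiveness and primary safety hypotheses, we require a sample size of 102 mITT subjects". The number refers to subjects with full 30-day follow-up. With 10% dropout assumed, the final size is 112.

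SAP 6.2 then makes study success conditional on "both primary effectiveness and safety objectives are met using the mITT Set". Neither document gives a probability of meeting both objectives or an assumption about how the two endpoints depend on each other.

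**The concern.** The two sizing sentences run in parallel, but only the safety one says *at least*. The effectiveness sentence gives 90% as what 101 subjects provide and 101 as the number required. Both parts can be checked against the plan's own test.

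The second issue is the success rule. When success needs two endpoints, the chance of success cannot exceed the smaller of the two powers and is usually below it. A section that claims to power both endpoints together, and prints only 90% figures, invites a reader to take 90% as the chance of a successful study at 102. The plan offers no calculation for that. Because the 30-day report supports a 510(k) submission, its sizing statement should be reproducible from the text.

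**Working it through.** **Inputs (all from SAP section 4; the same in protocol 8.1).** Effectiveness: p0 = 0.86, p1 = 0.96. Safety: p0 = 0.85, p1 = 0.95. Exact test, one-sided 0.025. The decision rule in SAP 6.2.2 and 6.2.5, a lower 95% Clopper-Pearson bound above the goal, gives the same critical values as this test.

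**Formulas.** The critical count r is the smallest r with P(X ≥ r | n, p0) ≤ 0.025. Power is P(X ≥ r | n, p1).

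**Step 1: the plan's effectiveness figure.** At n = 101:

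- r = 93 has type I error 0.0456, which is too large. r = 94 has 0.0214, so success needs at least 94 of 101, or at most 7 failures.
- Power = P(X ≥ 94 | 101, 0.96) = **0.9501**, against the stated 90%.

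Exact power moves in a sawtooth as n grows, so the required number depends on the convention used:

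| n | Successes needed | Type I error | Power |
|---|---|---|---|
| 89 | 84 | 0.0105 | 0.8536 |
| 90 | 84 | 0.0242 | 0.9308 |
| 98 | 92 | 0.0117 | 0.9018 |
| 99 | 93 | 0.0106 | 0.8977 |
| 100 | 93 | 0.0234 | 0.9525 |
| 101 | 94 | 0.0214 | 0.9501 |
| 102 | 95 | 0.0197 | 0.9477 |
| 112 | 104 | 0.0189 | 0.9639 |

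90% is first reached at n = 90. It is held from n = 100 (checked up to 124). Neither convention gives 101, although the second comes within one subject. A normal approximation with the null variance for alpha gives 87 for 90% power (97 with continuity correction) and 101 for 95% power. The plan specifies the exact test, so that last match does not show how 101 was obtained.

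**Step 2: the plan's safety figure.**

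| n | Event-free subjects needed | Type I error | Power |
|---|---|---|---|
| 101 | 94 | 0.0110 | 0.8667 |
| 102 | 94 | 0.0231 | 0.9303 |
| 112 | 103 | 0.0206 | 0.9456 |

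Power first reaches 90% at 93 (0.9059), dips below it at 95 (0.8968) and holds from 102. The stated 102 with at least 90% therefore reproduces.

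**Step 3: joint power for the success rule.** Let E and S be the two powers. Under independence joint power is E × S. Under any dependence it lies between E + S − 1 and min(E, S).

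- n = 102: 0.9477 × 0.9303 = **0.8817**. Lower bound 0.9477 + 0.9303 − 1 = 0.8780; upper bound 0.9303.
- n = 112: 0.9639 × 0.9456 = **0.9115**. Lower bound 0.9639 + 0.9456 − 1 = 0.9095; upper bound 0.9456.

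**Step 4: the completer count.** 112 × 0.90 = 100.8, about 101, which is short of the 102 completers that the section asks for. Dividing instead, 102 / 0.90 = 113.3, which rounds up to 114. Because of the sawtooth, one subject matters here: safety power is 0.9303 at 102 and 0.8667 at 101.

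**The case against.** The strongest reply is that this is wording and not a design fault. The 90% in the effectiveness sentence can be read as a target floor, and 101 is one subject from the 100 at which that floor holds. The shortfall in the stated figure is on the safe side, and safety, not effectiveness, sets the overall 102. All of this stands. It limits the consequence, but the sentence still gives neither the power at 101 nor the number required for 90%.

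Four stronger readings are tempting, and the documents do not support them.

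- *Both power statements are wrong.* The safety statement is right.
- *Effectiveness needed only 90 subjects.* That is one peak of the sawtooth; power is back under 90% at 99.
- *The plan claims 90% joint power and has only 88%.* Neither document prints a joint power, so 88.2% contradicts no stated number. It also needs independence and applies at 102. SAP 6.2.2 puts all mITT subjects in the safety denominator and counts early dropouts without an event as event-free. SAP 6.2.5 takes technical success over the mITT subjects, and that endpoint is settled at the procedure. With 112 analysed, joint power passes 90% whatever the dependence.
- *Dropout cuts joint power to 82.4%* (0.9501 × 0.8667 at 101). This removes 30-day dropouts from both endpoints. If they leave safety only, as in the complete-case sensitivity analysis of SAP 6.2.4, the figure is 0.9639 × 0.8667 = 83.5% under independence. Neither figure describes the primary analysis.

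**Conclusion.** The point holds in a limited form. One stated power is wrong: effectiveness at 101 is 95.0%, an understatement of 5 percentage points in the conservative direction. One needed figure is missing: the joint power behind a two-endpoint success rule. It is 88.2% at 102 under independence (87.8% to 93.0% over all dependence) and 91.15% at 112 (at least 90.9%, at most 94.6%).

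The results rest on the plan's assumed rates of 96% and 95%. The figures at 112 also need all 112 subjects to be in the mITT set and assessable for both endpoints. SAP section 2 words 112 as an upper limit, and SAP 6.1.6 by default leaves out subjects with a missing value, so fewer assessable angiograms would change the effectiveness figure.

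No test, threshold or study conclusion changes, and the study is not shown to be undersized.

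**What to change.** Change the text in the protocol synopsis, protocol 8.1 and SAP section 4; add no subjects.

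1. For effectiveness, replace the 90% power wording with: *at least 90% (exact 95.0% at 101; 96.4% at 112)*, and stop describing 101 as the number required for 90%.
2. In the overall sample size paragraph, add: *Power to meet both objectives, assuming independent endpoints, is 88.2% at 102 mITT subjects (87.8% to 93.0% under any dependence) and 91.15% at 112 (at least 90.9%).*
3. In the same paragraph, correct the completer count: 112 less 10% is about 101, not 102. Give the safety power at 101 (86.7%), labelled as a complete-case figure, and note that the primary safety analysis keeps all mITT subjects in the denominator.

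The cost is a few sentences in two documents. The sponsor discloses one less favourable number, at 102, beside one above 90% at the planned size.
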